6.2.4 Cisplatin Modifications

6.2.4.1 Blood/Bone Marrow (Hematologic) Adverse Effects

Granulocyte, ANC or Platelet Counts

Based on counts within 2 days prior to each scheduled cisplatin dose, give the following:

ANC or granulocytes/μL		Platelets/μL	Cisplatin
$\geq 1,500$	and	$\geq 100,000$	No Dose Reduction
1,499-1,000	or	99,999-75,000	Reduce by one dose level*
< 1,000	or	< 75,000	Hold*

Treatment should resume as soon as recovery from toxicity allows. If treatment is delayed for >2 weeks, notify the Study Chair. External RT should continue while drug is withheld.

*If the maximum number of prior dose reductions of cisplatin have been made, treatment may be held for up to two weeks for blood count recovery. Treatment will resume at the same dose level as there are no more dose reductions allowed.

Nadir blood counts or febrile neutropenia

For nadir neutropenia in the absence of fever or with fever which is successfully treated by oral antibiotics, there will be no dose adjustment.

Hold cisplatin during febrile neutropenia. For febrile neutropenia (ANC $\leq 500/\text{mm}^3$ ($0.5 \times 10^9/\text{L}$) and temperature $\geq 100.5^\circ\text{F}$ or 38°C) requiring intravenous antibiotics, the dose of cisplatin should be reduced by 1 dose level for the next and subsequent doses of chemotherapy.

For Grade 4 nadir thrombocytopenia (platelets $\leq 10,000$ ($10.0 \times 10^9/\text{L}$)), the dose of cisplatin should be reduced by 1 dose level for the next dose and for all subsequent doses of chemotherapy.

6.2.4.2 Gastrointestinal Toxicity

Diarrhea is more likely attributable to radiation treatment in this setting. The cisplatin dose will **not** be reduced for diarrhea.

All patients should receive antiemetics to prevent nausea and vomiting. Specific antiemetic therapy is left to the discretion of the investigator. If vomiting is severe, study subjects may require hospital admission and

treatment with any effective antiemetic regimen. Cisplatin doses will NOT be modified for nausea or vomiting.

6.2.4.3 Weight Loss

If a subject has weight loss of more than 10% from their baseline weight at enrollment while receiving cisplatin/RT, the BSA for the cisplatin dose will be recalculated based on the new weight for the remainder of the cisplatin doses.

6.2.5 Nephrotoxicity

If serum creatinine is ≥ 1.5 mg/dL (133 μ mol/L) on the planned treatment date, estimate the creatinine clearance (CrCl) by the Cockcroft and Gault Equation for women:

$$\text{CrCl (mL/min)} = (140 - \text{age in years}) \times (\text{Weight in kg} \times 0.85) / (72 \times \text{serum creatinine})$$

Denominator for SI units (mL/s) = $(48816 \times \text{serum creatinine in } \mu\text{mol/L})$

Calculated Creatinine Clearance (CrCl)	Management
< 60 but ≥ 50 mL/min (<1.00 but ≥ 0.84 mL/s)	Hydrate as clinically indicated. Treatment with cisplatin may continue at a one level reduction in the cisplatin dose.
< 50 but ≥ 40 mL/min (< 0.84 but ≥ 0.67 mL/s)	Hold cisplatin for one week and hydrate as clinically indicated. If repeat CrCl ≥ 50 mL/min (0.84 mL/s) after one week, may resume with a one level reduction in the cisplatin dose. If CrCl does not recover to ≥ 50 mL/min (0.84 mL/s) within one week, permanently discontinue cisplatin.
< 40 mL/min (< 0.67 mL/s)	Permanently discontinue cisplatin.

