3.1 Inclusion Criteria

- 3.1.1 Participants (who have been adequately clinically staged by standard clinical guidelines) with primary, untreated, histologically-confirmed, documented invasive squamous cell carcinoma, adenocarcinoma, or adenosquamous carcinoma of the uterine cervix, FIGO stages IB2, IIA, IIB, IIIA, IIIB, and IVA. (Stage IIA tumors must be greater than 4 cm.)
- 3.1.2 HIV-1 infection, documented by any licensed rapid HIV test or HIV enzyme or chemiluminescence immunoassay (E/CIA) test kit at any time prior to study entry and confirmed by a licensed Western blot or a second antibody test by a method other than the initial rapid HIV and/or E/CIA, or by HIV-1 antigen, plasma HIV-1 RNA viral load.

NOTE: The term “licensed” refers to a U.S FDA-approved kit or for sites located in countries other than the United States, a kit that has been certified or licensed by an oversight body within that country and validated internally.

WHO (World Health Organization) and CDC (Centers for Disease Control and Prevention) guidelines mandate that confirmation of the initial test result must use a test that is different from the one used for the initial assessment. A reactive initial rapid test should be confirmed by either another type of rapid assay or an E/CIA that is based on a different antigen preparation and/or different test principle (e.g., indirect versus competitive), or a Western blot or a plasma HIV-1 RNA viral load.

- 3.1.3 The following laboratory tests within 14 days of study enrollment:
 - Hemoglobin \geq 10 g/dL (6.2 mmol/L)
 - Platelet count \geq 100,000/mm³ ($100 \times 10^9/L$)
 - ANC \geq 1500/mm³ ($1.5 \times 10^9/L$) (Participants receiving transfusion, erythropoietin, or myeloid growth factor support will be eligible for this study)
 - Creatinine clearance \geq 60 mL/min (1.00 mL/s) calculated by the Cockcroft-Gault equation for women
 - AST and ALT \leq 3 X ULN
 - Total bilirubin \leq 2 X ULN unless related to antiretroviral use (e.g., atazanavir and indinavir), then the direct bilirubin must be \leq 2 X ULN

- 3.1.4 Adults, 18 years of age or older. DOB and age should be determined based on best possible information or documentation available.

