4.3 Chemotherapy

4.3.1 Cisplatin (Platinol®-AQ –NSC #119875)

4.3.1.1 Formulation: Cisplatin is supplied as a sterile aqueous solution, each ml containing 1 mg cisplatin and 9 mg sodium chloride. Cisplatin is supplied in multidose vials containing either 50mg or 100mg of cisplatin.

NOTE: Aluminum reacts with cisplatin causing precipitation formation and loss of potency; therefore, needles or intravenous sets containing aluminum parts that may come in contact with the drug must not be used for the preparation or administration of cisplatin.

4.3.1.2 Storage: Store at 15 to 25°C. Do not refrigerate. Protect unopened container from light. The cisplatin remaining in the amber vial following initial entry is stable for 28 days protected from light or for 7 days under fluorescent room light.

4.3.1.3 Adverse effects: Leukopenia, thrombocytopenia, anemia, nausea, vomiting, nephrotoxicity, ototoxicity, peripheral neuropathy, electrolyte imbalance, hypocalcemia, hypomagnesemia, aminoglycoside ototoxicity, ocular toxicity, and allergic reactions.

Infrequent: Cardiac abnormalities, anorexia, elevated SGOT, rash, alopecia, and acute myeloid leukemia.

NOTE: Aminoglycoside antibiotics given before, with, or after cisplatin may potentiate renal toxicity and should be avoided whenever possible. Gentamicin ototoxicity is also potentiated by cisplatin and should be avoided whenever possible.

Severe renal toxicity can be largely avoided by induction of diuresis before, during and after treatment. Mild renal dysfunction is a common complication (10%) of chronic therapy and may require discontinuation of therapy if BUN \geq 30 mg/dL (10.7 mmol/L) or creatinine clearance $<$ 40 mL/min (0.67 mL/s) or creatinine $>$ 2.0 mg/dL (177 μ mol/L) develop. If serum creatinine is \geq 1.5 mg/dL (133 μ mol/L) on the planned treatment date, please see cisplatin dose modifications in [Section 6.2](#).

- 4.3.1.4 Supplier: Cisplatin will be purchased commercially and provided by the AMC.

*Refer to Package Insert for additional information.

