5.2 Evaluations during Chemo-Radiation Treatment

5.2.1 Weekly During Chemo-Radiation (Day 1, 8, 15, 22, 29, 36, (- 2 days))

The following laboratory results will be obtained on the same day or up to 2 days prior to cisplatin administration unless otherwise noted:

- CBC and differential
- Calculated creatinine clearance
- Electrolytes (sodium, potassium, chloride, magnesium)
- Review of interim medical history including concomitant medications and adverse events
- ART adherence assessment will be collected on Day 8, Day 15, Day 22, Day 29, and Day 36.

- Physical Examination on Day 22 prior to treatment.

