6.2.3 Dose Modifications for Cisplatin

If different dose levels for cisplatin are required because of two different types of toxicities, use the dose level requiring the greatest reduction. There will be no dose re-escalation once the cisplatin is dose reduced.

The following levels should be used for cisplatin dose reductions:

Dose Level 0	Dose Level -1	Dose Level -2
40 mg/m^2	30 mg/m^2	25 mg/m^2

There will be no dose reduction below dose level -2 (i.e. cisplatin will be discontinued if further toxicity occurs).

Chemotherapy should not be administered during a radiation therapy delay.

All chemotherapy-related toxicities will also be graded according to the Common Toxicity Criteria (CTCAE v4.0).

Radiotherapy will not be omitted or delayed for chemotherapy-related toxicities unless the investigator considers that the participant is too sick to be treated.

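### The renal dose table is opened by serum creatinine of 1.5 mg/dL or more, so creatinine clearance of 40-59 mL/min below that creatinine carries no mandatory cisplatin reduction or hold

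*Combined protocol and SAP*

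**What the plan says.** Three places in the protocol are keyed to calculated CrCl:

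- **Eligibility (3.1.3).** CrCl of at least 60 mL/min, "calculated by the Cockcroft-Gault equation for women".
- **Weekly tests (5.2.1).** Calculated CrCl is listed for days 1, 8, 15, 22, 29 and 36, under this instruction: "The following laboratory results will be obtained on the same day or up to 2 days prior to cisplatin administration unless otherwise noted". No creatinine condition is attached.
- **Dose table (6.2.5).** For CrCl below 60 but at least 50: "Treatment with cisplatin may continue at a one level reduction in the cisplatin dose". For CrCl below 50 but at least 40: "Hold cisplatin for one week and hydrate as clinically indicated", then resume one level lower if CrCl is back to 50, otherwise stop. For CrCl below 40: stop permanently.

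The way into that table is keyed to serum creatinine. Section 6.2.5 says that if creatinine is 1.5 mg/dL or more, sites should act "on the planned treatment date, estimate the creatinine clearance (CrCl) by the Cockcroft and Gault Equation for women". Section 4.3.1.3 uses the same threshold: at that creatinine "on the planned treatment date, please see cisplatin dose modifications in" Section 6.2.

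The only other renal dosing text is in 4.3.1.3. Renal dysfunction "may require discontinuation of therapy if BUN" is 30 mg/dL or more, CrCl is below 40 mL/min, or creatinine exceeds 2.0 mg/dL. Section 8.1.5 lets the investigator stop treatment on clinical grounds.

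**The concern.** CrCl depends on age and weight as well as creatinine, so a fixed creatinine of 1.5 mg/dL corresponds to very different clearances in different women. In a light or older woman, clearance can fall through the reduce and hold bands while creatinine is still below 1.5. The text as written then requires no action, although the protocol's own table says to reduce or hold at that clearance.

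This is a matter of patient safety. A woman who entered with CrCl of at least 60 could receive unreduced cisplatin, a nephrotoxic drug, at a clearance where the protocol intends otherwise. Section 4.2.3.2 notes that tenofovir may worsen cisplatin-related renal insufficiency and asks sites to avoid it where possible, but does not prohibit it. There is also a consistency problem: one site may follow the creatinine condition and another may apply the rows to the weekly CrCl.

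**Working it through.** **Inputs.** The formula is the one in 6.2.5: CrCl (mL/min) = (140 − age) × weight × 0.85 / (72 × creatinine in mg/dL). The band limits 60, 50 and 40 and the trigger of 1.5 come from the same section. The documents give no age or weight distribution, so the ages and weights below are assumptions. There is no design figure to reproduce; the check is whether the bands fall below the trigger.

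**Step 1: creatinine at which each limit is crossed, age 45.** Rearranged, creatinine = 95 × weight × 0.85 / (72 × CrCl). At 50 kg the numerator is 4037.5, giving 4037.5/4320 = 0.93, 4037.5/3600 = 1.12 and 4037.5/2880 = 1.40.

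| Weight | CrCl 60 | CrCl 50 | CrCl 40 | CrCl at creatinine 1.5 | Row when the table opens |
|---|---|---|---|---|---|
| 50 kg | 0.93 | 1.12 | 1.40 | 37.4 | stop |
| 60 kg | 1.12 | 1.35 | 1.68 | 44.9 | hold |
| 70 kg | 1.31 | 1.57 | 1.96 | 52.3 | reduce |

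At 50 kg the reduce band (creatinine 0.93-1.12) and the hold band (1.12-1.40) both lie wholly below 1.5. From just above 1.40 up to 1.5 her CrCl is already below 40, where only the permissive text applies. At 60 kg the reduce band is missed. At 70 kg the reduce row is reached, but not for creatinine between 1.31 and 1.5.

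**Step 2: weight needed for a given CrCl at creatinine 1.5.** Weight = CrCl × 72 × 1.5 / (0.85 × (140 − age)).

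| Age | Hold band also missed below | Reduce band wholly missed below | No gap at or above |
|---|---|---|---|
| 30 | 46.2 kg | 57.8 kg | 69.3 kg |
| 45 | 53.5 kg | 66.9 kg | 80.2 kg |
| 60 | 63.5 kg | 79.4 kg | 95.3 kg |

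**Step 3: does other text cover the gap?** Section 4.3.1.3 is permissive, and its CrCl limit starts below 40, so it is silent on 40-59. Section 6.2.5.4.1 covers only Grade 3 or 4 toxicity not dealt with earlier. Section 8.1.5 is investigator discretion. None makes a reduction or hold mandatory at CrCl 40-59.

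**Step 4: the SI version of the formula.** Section 6.2.5 prints a denominator of 48816 per µmol/L for a result in mL/s. Section 4.3.1.3 equates 2.0 mg/dL with 177 µmol/L, or 88.5 per mg/dL, so the expected constant is 72 × 60 / 88.5 = 48.8. The printed value is about 1000 times larger. At age 45, 60 kg and 133 µmol/L it gives 4845 / (48816 × 133) = 0.00075 mL/s, where 48.8 gives about 0.75. This may be an artefact of text extraction.

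**The case against.** The best counter-argument is that the opening sentence says when to estimate CrCl, not that the rows apply only then. The rows carry no creatinine condition, and the weekly CrCl from 5.2.1 has no other stated dosing use, so a sensible site would apply the table to it. That reading is available, and some sites may follow it. But it leaves the creatinine condition with no work to do, since CrCl is already calculated before every dose, and the condition is stated in two sections. The text does not tell a site which reading to choose.

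It is also fair to say that 4.3.1.3 and 8.1.5 offer some protection. They do, at CrCl below 40 or on clinical judgement, but neither prescribes an action at 40-59.

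A reader might also infer that the table leaves women already at Dose Level -2 without a rule, because it calls for a one-level reduction that does not exist there. The documents do not support that. Section 6.2.3 sets a general floor: no reduction below Dose Level -2, with cisplatin discontinued on further toxicity. The resume-at-the-same-level note in 6.2.4.1 is an exception for blood counts only, and the neurotoxicity rule in 6.2.5.2 also ends in discontinuation at that level.

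**Conclusion.** The mismatch is real and should be fixed. Read as written, CrCl 40-59 with creatinine below 1.5 mg/dL has no mandatory reduction or hold, and CrCl below 40 with creatinine below 1.5 has no mandatory stop. That the gap exists follows from the protocol's own formula. Its extent for any woman depends on age and weight: at age 45 it is widest at low weight and closes at about 80 kg.

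Two further inferences go beyond the documents. One is that many women will be overdosed: without an age or weight distribution, and without knowing how sites read the sentence, the number cannot be estimated. The other is that the treatment completion rate is biased in a known direction: earlier reductions, holds and stops could change completion either way, and the net effect is uncertain.

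**What to change.** In 6.2.5, delete the creatinine trigger and write: *Apply the row matching the Cockcroft-Gault CrCl obtained on the day of, or up to 2 days before, each cisplatin dose (Section 5.2.1), whatever the serum creatinine.* In 4.3.1.3, refer the reader to 6.2.5 when CrCl is below 60 mL/min. While editing, check the SI denominator against the source file. Dose Level -2 needs no change.

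The cost is wording in two places and no new test. The clinical downside is that some women will be reduced, held or stopped earlier, and reductions are permanent: "There will be no dose re-escalation once the cisplatin is dose reduced". For a 45-year-old, the mandatory stop moves from creatinine 1.5 to just above 1.40 at 50 kg, and the hold moves from 1.5 to just above 1.35 at 60 kg. Women who enter just above CrCl 60 are the most exposed: at age 45 and 50 kg, creatinine 0.93 gives CrCl 60.3 and 0.94 gives 59.7, which is the reduce row. The current text already has such a step for an 80 kg woman of 45, from 60.2 at creatinine 1.49 to 59.8 at 1.50. These are the actions the protocol already prescribes at those clearances.

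### The renal dose table opens only at serum creatinine of 1.5 mg/dL or more, which does not match its own clearance bands or the clearance obtained before every dose, so one recorded result can support different cisplatin actions

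*Combined protocol and SAP*

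**What the plan says.** Section 6.2.5 (Nephrotoxicity) opens with a condition, "If serum creatinine is ≥ 1.5 mg/dL", and then a step: "on the planned treatment date, estimate the creatinine clearance (CrCl) by the Cockcroft and Gault Equation for women". A table of actions follows, banded on that clearance:

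- "< 60 but ≥ 50 mL/min": cisplatin may continue one dose level lower.
- "< 50 but ≥ 40 mL/min": hold for one week and repeat; resume one level lower if clearance is back to at least 50, otherwise stop cisplatin permanently.
- Below 40 mL/min: stop cisplatin permanently.

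Section 4.3.1.3 repeats the 1.5 mg/dL condition when it sends the reader to Section 6.2. Three provisions do not carry it:

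- Section 5.2.1 lists "Calculated creatinine clearance" among the laboratory results due on the day of each cisplatin dose or up to two days before, for every participant.
- Section 3.1.3 sets entry at a clearance of at least 60 mL/min, "calculated by the Cockcroft-Gault equation for women", with no creatinine limit.
- Section 4.3.1.3 says: "Mild renal dysfunction is a common complication (10%) of chronic therapy and may require discontinuation of therapy if BUN" reaches 30 mg/dL, or clearance falls below 40 mL/min, or creatinine exceeds 2.0 mg/dL. The three are alternatives, so clearance below 40 counts there without reference to 1.5 mg/dL.

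**The concern.** A clearance result will be on file before every dose, but the protocol does not say what to do when it lies in the reduction or hold band and creatinine is below 1.5 mg/dL. Read literally, Section 6.2.5 changes nothing. Read by its bands, it reduces or holds. For clearance below 40 with creatinine below 1.5, the mandatory stop in Section 6.2.5 is not reached, while Section 4.3.1.3 says only that discontinuation may be required.

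Two things are at stake. One is renal safety with a drug whose nephrotoxicity the protocol itself describes. The other is the primary outcome: Section 11.1 counts women who complete cisplatin among those who start it, so a permanent stop under one reading and continued dosing under the other can classify the same woman differently. Sites could differ on this without either departing from the text.

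**Working it through.** **Inputs.** From Section 6.2.5: the 1.5 mg/dL gate, the cuts at 60, 50 and 40 mL/min, and the equation CrCl = (140 − age) × weight × 0.85 / (72 × creatinine). From Section 11.2: 38 evaluable women. The documents give no distribution of age, weight or creatinine. The only hint is a remark in Section 1.0 that these patients are often poorly nourished.

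**Step 1: where each cut falls on the creatinine scale.** Rearranged, creatinine = (140 − age) × weight × 0.85 / (72 × CrCl).

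| Woman | reaches 60 at | reaches 50 at | reaches 40 at | CrCl at 1.5 mg/dL |
|---|---|---|---|---|
| 45 y, 60 kg | 1.12 | 1.35 | 1.68 | 44.9 |
| 50 y, 50 kg | 0.89 | 1.06 | 1.33 | 35.4 |

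For the first woman, the whole reduction band and the hold band from 50 down to 44.9 lie below the gate. Every stop-band value lies above it. The second woman is eligible at creatinine 0.8: 90 × 50 × 0.85 / (72 × 0.8) = 66.4. At 1.2 her clearance is 44.3 (hold band) and at 1.4 it is 37.9 (stop band). Neither value opens the table.

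**Step 2: which weights are affected.** Setting creatinine to 1.5 gives weight = CrCl × 108 / (0.85 × (140 − age)). At age 45 this is 80.2 kg for 60 mL/min, 66.9 kg for 50 and 53.5 kg for 40. Hence at age 45:

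- Reduction band: wholly below the gate under 66.9 kg, not at all from 80.2 kg.
- Hold band: wholly below under 53.5 kg, partly from 53.5 to 66.9 kg, not at all from 66.9 kg.
- Stop band: values can be missed only under 53.5 kg. That limit is 46.2 kg at age 30, 56.5 kg at 50 and 63.5 kg at 60.

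Steps 1 and 2 need no population assumption.

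**Step 3: one value, two actions inside Section 6.2.5.** Take the 45-year-old, 60 kg woman at creatinine 1.4: 95 × 60 × 0.85 / (72 × 1.4) = 48.1 mL/min. Arriving there from a lower creatinine, she does not open the table and nothing changes. If she was held at 1.5 (44.9) and 48.1 is her repeat a week later, it is below 50 and cisplatin stops permanently.

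**Step 4: how many women in a band miss the gate.** Assumptions: mean age 43-45 (SD 9), mean weight 55-65 kg (SD 10-13), clearance uniform within each band. The last column widens this to mean age 40-50 (SD 10) and mean weight 50-75 kg (SD 12).

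| Band (mL/min) | Share with creatinine < 1.5 | Wider assumptions |
|---|---|---|
| Reduction, 50-60 | 69-94% | 38-97% |
| Hold, 40-50 | 35-68% | 11-84% |
| Stop, 30-40 | 10-25% | 1-50% |
| Hold and stop pooled, 30-50 | 22-46% | 6-67% |

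**Step 5: leverage on the primary outcome.** Each woman whose completion turns on the reading moves the rate by 1/38 = 2.6 percentage points. The documents do not allow an estimate of how many such women there would be.

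**The case against.** The strongest defence is that the worst case is not left open. Section 4.3.1.3 names clearance below 40 without the gate, Section 8.1.5 lets the investigator stop treatment that no longer serves the participant, and a woman whose creatinine keeps rising will reach 1.5 at a later weekly check. The different actions in Step 3 could also be deliberate, with recovery after a hold judged more strictly than first entry. All of this has weight. But the first two routes are discretionary and do not cover the reduction and hold rows, the third delays the action by one or more doses, and no text says that Step 3 is intended.

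A reader might infer more: that most women whose clearance has fallen into the hold or stop bands never trigger the table. The documents do not support that. Under the Step 4 assumptions, about 83-98%, 53-85% and 19-46% of all women would have clearance below 60, 50 and 40 when creatinine stands at exactly 1.5. Those figures show how often a band could be entered unnoticed. They do not give the share of women in a band who are missed. That share is 22-46% for hold and stop pooled, and passes half only under the lighter or older of the wider assumptions. Never is also too strong, for the reasons above.

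It is also fair to object that Sections 9.1.1 and 11.1 do not define completion by number or dose of cycles. A reduction or a one-week hold therefore need not count as failure, whereas a permanent stop would.

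**Conclusion.** The inconsistency stands. The creatinine gate in Section 6.2.5, repeated in Section 4.3.1.3, does not fit the clearance bands it opens, the clearance obtained before each dose, the clearance-based entry criterion, or the ungated mention of clearance below 40. That follows from the text and the protocol's own equation.

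Its size depends on assumed age and weight. Most women in the reduction band would miss the table under the main assumptions (69-94%). In the hold band it is roughly a third to two thirds (35-68%), and in the stop band a minority (10-25%, for 30-40 mL/min), mainly lighter or older women. These shares rest on outside assumptions about age and weight and on clearance being uniform within each band. The effect on the completion rate is possible, at 2.6 points per woman affected, but its total is unknown. The point deserves correction because it bears on safety and the remedy is cheap, not because a large bias has been shown.

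**What to change.** Reconcile Sections 6.2.5, 4.3.1.3, 5.2.1 and 3.1.3 so that a single trigger for the renal table is stated in the same words wherever it appears, and so that the repeat value after a hold is read consistently with first entry or the difference is stated as intended. Which clinical rule applies is for the sponsor's clinicians.

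In the completion analysis, flag each dosing occasion on which the creatinine condition and the clearance bands would lead to different actions, and report how many women's completion status depends on it.

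The cost is protocol wording plus one derived flag; weekly clearance is already collected. Depending on the reading chosen, the stated completion rate may be slightly lower.
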